For subjects who received CVnCoV, the end of trial visit will be performed on Day 393, 1 year after the last trial vaccine administration. For subjects who received placebo, the end of trial visit will be conducted after unblinding. If possible, this visit should also include subjects who prematurely discontinued vaccination during the trial. The following assessments should be performed:

- Review and record any newly reported AEs since the phone contact on Day 302 (SAEs).
- Record concomitant medications and vaccinations, according to instructions in Section 7.6.
- Record symptoms suggestive of COVID-19 or any confirmed COVID-19 case.
- Perform a complete physical examination, including height and weight (see Section 9.3.6).
- Measure vital signs (body temperature, pulse, blood pressure, see Section 9.3.6).

**9.1.2 All Other Subjects and subjects that, following unblinding, receive an authorized vaccine after having received at least one dose of CVnCoV**

Following enrollment of subjects into the Immunogenicity/Reactogenicity Subset (n=1,260), the remaining 1,260 subjects, 18 years of age and older, will be enrolled to this group.

Also, all subjects initially enrolled to the Immunogenicity/Reactogenicity Subset that receive an authorized vaccine following at least one dose of CVnCoV will be included in this group from the day when the authorized vaccine is administered (Schedule of Activities- Table 2).

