
 Occurrence, intensity and relationship of unsolicited AEs occurring within 28 days after each trial vaccination in a subset of subjects. 	
 Each solicited systemic AE within 7 days after each trial vaccination by intensity, by relationship to trial vaccine and overall. At least 1 unsolicited AE, at least 1 grade 3 unsolicited AE and each unsolicited AE by SOC/PT occurring within 28 days after each trial vaccination and overall by causal relationship to trial vaccine and overall. 
The mean duration in days by group with standard deviation (SD) of solicited AEs is described.

Primary Immunogenicity	

SARS-CoV-2 RBD of S protein antibody responses
 
On Days 1, 29 and 43:
 
 Serum antibodies to SARS-CoV-2 RBD of S protein. Occurrence of seroconversion to SARS-CoV-2 RBD of S protein 
 Seroconversion is defined as detectable SARS-CoV-2 RBD of S protein antibodies in the serum of subjects who tested seronegative at baseline. 	
In subjects belonging to the Immunogenicity/Reactogenicity subset and evaluable {complying with the definition of PPI Subset}:
 
On Days 1, 29 and 43:
 
 Geometric Mean of Titers (GMTs) with 95% Confidence Interval (CI) of SARS-CoV-2 RBD of S protein antibody responses by group and by baseline serostatus. 
On Days 29 and 43 for subjects seronegative at baseline:
 
 Number and percentage with exact 95%CI of subjects by group for whom a seroconversion is observed (detectable SARS-CoV-2 RBD of S protein antibodies in the serum).
Secondary Efficacy	

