 - If date of resolution is completely missing, and it is assumed that it resolved at the date of the end of the trial, the date of the end of the trial is used as the AE end date.
 - If year is present, it is assumed that it resolved on 31 December of that year (i.e., 31DECYYYY), or at the end of the trial if this is earlier and in the same year.
 - If year and month are present, it is assumed that it resolved on the last day of that month, or at the end of the trial if this is earlier and in the same month/year.
- Imputation of missing AE start times:
 - If the (recorded or imputed) AE start date is equal to the vaccination start date, then the AE start time is the time of vaccination start.
 - In all other cases, AE start time is imputed as 00:00.

If not stated otherwise, the original or incomplete data is presented in listings rather than the imputed one.

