10.5.3 Duration and Time of Onset for Solicited AEs

Duration of solicited local and systemic AEs is defined as the number of **consecutive** days with a recorded local/systemic AE regardless of grade. For example, Fatigue with Grade 1 occurring on day 2 and 3 and day 7 is counted as two separate events with the duration 2 days and 1 day.

The duration of solicited local and systemic AEs ongoing beyond Day 8 after vaccination is defined as

$$\text{Duration} = \text{AE end date} - \text{AE start date} + 1.$$

The AE end date as recorded on the CRF is used in the above formula except for instances where the recorded date is incomplete in which case the imputed date is used.

The time of onset (Day) of a solicited AE is defined as the day of first occurrence of the AE after the trial vaccination it was assigned to (dose 1 or dose 2, see also Section 10.5.2), regardless of the severity (Grade 1 – Grade 3). The time of onset (Day) of a Grade 3 solicited AE is defined as the first day after the trial vaccination it was assigned to (dose 1 or dose 2, see also Section 10.5.2), on which the AE was first graded as severe (Grade 3), regardless of an earlier occurrence with a lower severity.

Durations are not calculated separately for each grade but rather only for any grade >0 (no matter how often it might transition up and down between grades 1 through 3) or grade=3. Only the longest consecutive duration determined this way is displayed.

Duration and time of onset are calculated separately for events recorded after each trial vaccination.

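### For solicited AEs still ongoing beyond Day 8, an end date imputed as the end of the trial or 31 December can enter the reported duration

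*SAP*

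**What the plan says.** - **Missing end dates.** For a completely missing AE resolution date, SAP 10.3 provides that "the date of the end of the trial is used as the AE end date". For a date with only the year: "If year is present, it is assumed that it resolved on 31 December of that year", or the end of the trial if that falls earlier in the same year.
- **Ordinary durations.** Under SAP 10.5.3 a solicited AE's duration is normally a count of consecutive "days with a recorded local/systemic AE regardless of grade". No end date is used.
- **Long-running events.** "The duration of solicited local and systemic AEs ongoing beyond Day 8 after vaccination is defined as" end date minus start date plus 1. The recorded end date is used, "except for instances where the recorded date is incomplete in which case the imputed date is used".
- **Display.** "Only the longest consecutive duration determined this way is displayed".
- **Summary.** SAP 9.4, Table 2: "The mean duration in days by group with standard deviation (SD) of solicited AEs is described". SAP 12.0 adds median, quartiles, minimum and maximum for continuous variables.
- **Protocol.** Section 10.3.9 rules out imputation of missing values except for partial dates of AEs and concomitant medication. SAP 6.1 lists 17 changes from the protocol; imputing wholly missing AE end dates is not among them.
- **Deliveries.** SAP 12.6.1.2 plans duration tables for local, systemic and related systemic AEs, overall and for Grade 3, then states that the EOT analysis contains no solicited-AE analyses. The footnote to SAP 6.0 and SAP 12.6.6 describe an earlier safety delivery, 6 weeks after dose 2.

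**The concern.** Duration of solicited local and systemic AEs is part of the primary safety endpoints (Protocol 4.2.1, SAP 9.1.1). These reactions are collected on the vaccination day and the following 7 days. A rule that can replace an unknown end date with one months later produces a value that reflects the length of follow-up, not the reaction. The longest-duration rule then makes that value the one shown for the subject, and a mean with SD is sensitive to it.

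SAP 10.3 is also uneven. It leaves a start date with no year missing because the uncertainty is too great, yet fills in an end date about which nothing is known.

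**Working it through.** **Inputs from the documents.** Dose 2 is on Day 29 and the end-of-trial visit on 29+364 (Protocol Table 1). For CVnCoV subjects, "the end of trial visit will be performed on Day 393, 1 year after the last trial vaccine administration" (Protocol 9.1.1.10), with a window of up to +21 days. The solicited-AE subset has 840 CVnCoV subjects, 420 per lot (Protocol 10.1.1). These are upper bounds for the number n with any one reaction.

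**Assumptions.** The documents give no typical duration and no rate of missing end dates. I take means m of 2 to 5 days, with m=3 and SD=2 as the main case.

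**1. The plan's own figure.** 29 + 364 = 393, as stated.

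**2. Imputed duration at the final end of trial** (end minus start plus 1):
- Dose 1, onset Days 1 to 8: 393−1+1 = 393 down to 393−8+1 = 386 days.
- Dose 2, onset Days 29 to 36: 393−29+1 = 365 down to 393−36+1 = 358 days.
- With the full +21 days (Day 414), the maxima are 414 and 386 days.

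**3. Effect of one 365-day record among n subjects with the event.** With M the new mean:
- M = ((n−1)m + 365)/n
- SD² = [(n−2)·SD₀² + (n−1)(m−M)² + (365−M)²]/(n−1), where SD₀ is the assumed SD.

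| n (m=3, SD₀=2) | Mean | SD |
|---|---|---|
| 10 | 39.2 | 114.5 |
| 50 | 10.2 | 51.2 |
| 100 | 6.6 | 36.3 |
| 200 | 4.8 | 25.7 |
| 420 | 3.9 | 17.8 |
| 840 | 3.4 | 12.6 |

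At n=420, M = (419×3+365)/420 = 3.86, a rise of about 0.9 day. At n=840, M = (839×3+365)/840 = 3.43, a rise of about 0.4 day.

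**4. When the mean doubles.** Setting M = 2m gives n = (365−m)/m: about 182 for m=2, 121 for m=3 and 72 for m=5.

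**5. An earlier cut, blank date.** The SAP does not say what stands for the end of the trial before it has occurred. If the cut date were used (assumption), a subject just 6 weeks past dose 2 with onset on the vaccination day would get 42+1 = 43 days (dose 2) or 28+42+1 = 71 days (dose 1). At m=3 and n=420 the mean moves by (43−3)/420 = 0.10 or (71−3)/420 = 0.16 day.

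**6. An earlier cut, year-only date.** Read literally, the 31 December rule does not wait for the trial to end. The footnote to SAP 6.0 gives 11 February 2021 as the last randomization date for that delivery. Taking this as Day 1, the latest in-window dose 2 is 28+7 days later, 18 March, and the latest onset 25 March, day 84 of the year. A year-only 2021 end date then gives 365−84+1 = 282 days, and more for earlier 2021 onsets. The mean moves by (282−3)/420 = 0.66 day. If the cut date counted as the end of the trial, this value would be truncated.

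**7. Text comparison.** SAP 10.5.3 brings in the imputed date when the recorded one is incomplete; SAP 10.3 treats completely missing dates as a separate case. Whether a blank date enters the formula is therefore left to the programmer. SAP 8.3 defines end of trial by the last subject, while placebo subjects are withdrawn early. If a subject-level date is used, the imputed value differs by arm.

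**The case against.** The strongest reply is that the year-long value has no identified table to appear in. SAP 12.6.1.2 removes solicited AEs from the EOT analysis, and at the 6-week delivery the end of the trial had not been reached. Which tables go to which delivery is set out in SAP Appendix 4, which is kept outside the SAP. This stands against any claim that final tables are distorted. It does not remove the rule: the duration tables remain planned, the change history records no revision of Section 10.3, and the year-only rule could act at an early cut.

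Other points also stand:
- The trigger is narrow: only solicited AEs ongoing beyond Day 8 without a usable end date.
- Missing dates should be few. Solicited AEs are reviewed at the Day 29 and Day 43 visits (Protocol 9.1.1.3, 9.1.1.5), missing data are queried (11.4), and AEs are followed until the outcome is known or nothing more can be learned (Appendix 10). Related Grade 3 reactions reported for more than one day are questioned for total duration (9.3.3.1), which partly protects the small Grade 3 rows.
- Median and quartiles are already planned. One extreme value hardly moves the median, and the maximum would expose it.

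A reader might infer that any missing resolution date adds a year and overwhelms the mean. The documents do not support that: most solicited durations use no end date, and for common reactions the mean moves by less than a day. A reader might also infer that the rule would decide the comparison between arms. Safety is descriptive, without formal testing (Protocol 10.3.5), and no missing-date rate is given.

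**Conclusion.** The point holds in a limited form. For solicited AEs ongoing beyond Day 8 with a missing or partial end date, the SAP permits a duration set by the calendar or the length of follow-up. For wholly missing dates this goes beyond Protocol 10.3.9 without being declared in SAP 6.1, although SAP 10.5.3 leaves its reach to blank dates unclear.

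Where the final end-of-trial date is used, one record is about 358 to 393 days. It inflates the SD at every n examined. It shifts the mean by about 0.9 day at n=420 and 0.4 day at n=840 (assumed mean 3 days), and at least doubles it only when roughly 70 to 180 or fewer subjects have the event (assumed means of 5 to 2 days), as may happen in Grade 3 rows. At a 6-week cut used as the end date, a blank date gives about 43 or 71 days. All shifts rest on assumed typical durations and on one affected record; the actual number is unknown.

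The exposure lies in deliveries of solicited duration other than the EOT analysis. It is a modest defect in a primary-endpoint derivation and easily corrected.

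**What to change.** In SAP 10.3 and 10.5.3:
1. Exclude solicited-AE durations from the end-of-trial and 31 December imputations, and say explicitly that this covers both blank and year-only dates.
2. End such a duration at the last date the AE was documented as present (diary or visit), flag it as censored, and give the number censored by group.
3. Lead the duration tables with the median and quartiles already planned, keeping mean and SD as secondary.
4. If wholly missing end dates are still imputed for other AEs, list that in SAP 6.1 as a change from Protocol 10.3.9, and define the date used at any cut before the trial ends.
5. Check any solicited-duration table already delivered for imputed end dates, and footnote or rerun it where they occur.

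The cost is a few sentences, a small program change and one check of past outputs. The drawback is that censored durations are lower bounds, so long reactions with unknown ends will be understated. The censored count makes that visible.

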10.4 Prior and Concomitant Medications

Medications are categorized as prior medication or concomitant medication based on the following rules:

- Any medication taken prior to trial start (informed consent signature) as recorded by the investigator is considered prior medication.
- Any medication **not** taken prior to trial start as recorded by the investigator is considered concomitant medication.
- Any medication taken prior to trial start as recorded by the investigator and for which “Ongoing” is ticked as “Yes” or “Unknown” is considered concomitant medication.

Note: A medication can be both prior and concomitant if it starts prior to trial start and is ongoing.

10.5 AEs

An AE is any untoward medical occurrence in a subject which does not necessarily have to have a causal relationship with the investigational product. In this trial, confirmed cases of COVID-19 and complications/sequelae are not considered as AEs as they are captured on the CRF pages for COVID-19 illness which are expected outcomes of the trial and are analyzed as efficacy endpoints.

In this trial, for subjects in the Immunogenicity/Reactogenicity Subset, information on solicited local and systemic AEs occurring within 7 days after each vaccination and on unsolicited AEs occurring within 28 days after each vaccination are collected.

For all trial subjects, information on medically attended AEs through 6 months after second vaccination and SAEs, AESIs and AEs leading to vaccine withdrawal or trial discontinuation through EOT are recorded.

Non-serious intercurrent medical conditions that may affect the immune response to vaccination are also collected as AEs throughout the trial.

No other AEs require recording in the CRF.

10.5.1 Treatment Emergent Adverse Events (TEAE)

A Treatment Emergent Adverse Event (TEAE) is any AE that first occurs or increases in severity or relationship to trial vaccine after the first dose of vaccine. AEs which change in severity or relationship to trial vaccine are assigned a new start date and captured as a new record in the CRF. Hence, an AE is defined as TEAEs if the start date/time is after the date/time of first vaccination. Imputed AE start date/time as defined in Section 10.3 is considered when assessing if an AE is treatment emergent. If the AE start date is still missing after applying imputation rules (i.e. missing year), the AE is considered treatment emergent and is assumed to occur within 28 days after any vaccination. However, it is not possible to link this event to a specific dose.

All Solicited AEs are considered treatment emergent, even in the case that (partially) missing or conflicting date/time information is recorded or imputed.

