### 10.3.5 Safety Analysis

No formal statistical testing of safety data is planned.

Safety endpoints will be described for each CVnCoV lot separately, for pooled lots, for placebo and overall.

**Solicited AEs:** The frequencies and percentages of subjects experiencing each solicited local and systemic AE within 7 days after each vaccination will be presented by intensity and overall. For subjects with more than 1 episode of the same AE within 7 days after a vaccination, the maximum intensity will be used for tabulations. Similar tabulations will be performed for solicited systemic AEs by relationship to trial vaccination. Solicited local AEs will be by definition considered as related to the trial vaccine. Time to onset (in days) and duration (in days) will also be summarized for each solicited local and systemic AEs. Summary tables showing the occurrence of at least 1 local or systemic solicited AE within 7 days after each vaccination will also be presented.

**Unsolicited AEs:** Unsolicited AEs including SAEs and AESIs will be coded using the Medical Dictionary for Regulatory Activities (MedDRA) by SOC and PT.

The frequency and percentage of subjects reporting at least 1 unsolicited AE within the 28 days after each vaccination and overall will be tabulated globally and for each SOC and PT levels.

Similar tables will be provided for: related unsolicited AE, Grade 3 or higher unsolicited AE, medically-attended AEs that occur within 6 months after the second trial vaccination, SAE, related SAE, AESI, related AESI, AEs leading to withdrawal or trial discontinuation and SAE resulting in death through 1 year after the second trial vaccination.

When an AE occurs more than once for a subject within the 29 days post 1 vaccination, the maximal severity and strongest relationship to the vaccine group will be counted.

Only AE post first vaccination will be considered in the summary tables. AE starting prior to the first vaccination will only be listed.

Data listings of fatal and SAEs will be provided by subject.

Vital signs will be summarized by descriptive statistics at each visit including change from baseline and a listing will be provided.

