10.3 Missing Data

In general, no imputation of missing values is done except for the following:

- Imputation of missing onset date for confirmed COVID-19 cases as specified in Section 10.7.2.
- For SARS-CoV-2 RBD of S protein antibodies, and viral neutralizing antibodies, concentration values marked as below the lower limit of quantification (LLOQ) are set to 0.5*LLOQ for computation purposes.
- Imputation of (partially) missing AE start dates:
 - If start date year value is missing, the date uncertainty is too high to impute a rational date. Therefore, if year value is missing, the imputed AE start date is set to missing.
 - If start date year value is before the vaccination start date year value, then the AE started before the vaccination. Therefore:
 - If month is missing, the imputed start date is set to the mid-year point (i.e., 01JULYYYY).
 - If month is not missing, the imputed start date is set to the mid-month point (i.e., 15MONYYYY).
 - If start date year value is equal to the vaccination start date year value, the start date month needs to be compared against the vaccination start date month, to determine the imputation rule to apply. Therefore:
 - If month is missing, the imputed month and imputed day is the same as start of vaccination
 - If month is lower than vaccination start date month and start date day is missing, the imputed start date is set to the mid-month point (i.e. 15MONYYYY).
 - If month is equal to the vaccination start date month and start date day is missing, the start day is set to the start day of vaccination.
 - If month is greater than the vaccination start date month and start date day is missing, the imputed start date is set to the beginning of the month (i.e., 01MONYYYY).
 - If start date year value is greater than the vaccination start date year value, the AE started after vaccination. Therefore:

- If month is missing, the imputed start date is set to the year start point (i.e., 01JANYYYY).
- If start date month is not missing and start date day is missing, the imputed start date is set to the beginning of the month (i.e., 01MONYYYY).
- If after imputation of start and resolution date (see below) a start date is after the resolution date (for example if a missing day of a start date is set to 15 and the resolution date is before the 15th of the same month and year) then the start date is set to the resolution date.
- Imputation of (partially) missing AE end dates:

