10.5.4 Unsolicited AEs

Information on unsolicited AEs occurring on each vaccination day (i.e. dose 1 and 2) and the following 28 days after each dose is collected for subjects in the Immunogenicity/Reactogenicity subset. Data is recorded in the eDiary by the subject to aid AE reporting. The investigator reviews the eDiary and records information on any AEs on the CRF.

Unsolicited AEs are assigned to first or second dose based on the (reported or imputed) AE date. Unsolicited AEs occurring before dose 2 are assigned to dose 1. Unsolicited AEs occurring after dose 2, are assigned to dose 2. Unsolicited AEs occurring on the day of dose 2 are assigned to either dose 1 or dose 2 as per the following rules:

- If the AE occurred on the day of dose 2 but before vaccination with dose 2, the AE is assigned to dose 1
- If the AE occurred on the day of dose 2 but on or after vaccination with dose 2, it is assigned to dose 2.
- If the AE occurred on the day of dose 2 and it cannot be determined whether it occurred before, on or after vaccination with dose 2, it is assigned to dose 2.

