12.6 Safety Analyses

12.6.1 Adverse Events

Unsolicited AEs, including SAEs, and AESIs and solicited AEs integrated to or recorded on the CRF are coded using MedDRA Version 23.1 or higher by SOC and PT.

Only TEAEs as defined in Section 10.5.1 are included in AE summaries. In AE listings, all AEs are included.

Solicited AEs occurring on the day of vaccination and the following 7 days are generally included in summaries if not otherwise stated.

Summaries of medically attended AEs only include those AEs that started up to 6 months after the second trial vaccination, see Section 10.5.6 for further details.

Note that for all summaries by SOC and PT, counting is by subject, not event and subjects are only counted once within each SOC and PT. However, if not stated otherwise, all summaries of unsolicited AEs include the number of AEs reported in each category and all events of a subject are then counted.

All AE summary tables are provided overall, by vaccine group (placebo, pooled CVnCoV lot, and split by lot), and are repeated separately in subjects seronegative at baseline and in subjects seropositive at baseline for SARS-CoV-2 N protein antibody levels (see Section 10.6.1).

In general, percentages are based on the number of subjects in the respective analysis set. In summary tables for AEs after the second vaccination, percentages are based on the number of subjects in the respective analysis set who have received the second vaccination.

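### Read literally, the SAP's imputation rules place some adverse events exactly at the time of first vaccination, and its strict 'after' test then keeps them out of the AE summary tables

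*SAP*

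**What the plan says.** Three SAP sections act in sequence.

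- **SAP 10.3 (Missing Data), start dates.** Where the start year equals the vaccination year: "If month is missing, the imputed month and imputed day is the same as start of vaccination". Where the month also matches the vaccination month and the "start date day is missing, the start day is set to the start day of vaccination".
- **SAP 10.3, missing clock times.** One rule covers dates as entered and dates filled in by imputation alike: "AE start date is equal to the vaccination start date, then the AE start time is the time of vaccination start". Any other missing time becomes 00:00.
- **SAP 10.5.1 (TEAE).** The imputed date and time are used, and "an AE is defined as TEAEs if the start date/time is after the date/time of first vaccination". There are two exemptions. Solicited AEs always count as treatment emergent, and so does an AE whose start date is still missing after imputation because the year is unknown.
- **SAP 12.6.1 (Adverse Events).** "Only TEAEs as defined in Section 10.5.1 are included in AE summaries". Listings include all AEs.

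Protocol 10.3.5 sets the parent rule in two sentences: "Only AE post first vaccination will be considered in the summary tables", and "AE starting prior to the first vaccination will only be listed". It does not say what to do with a start equal to the vaccination time.

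**The concern.** A start time that has been set equal to the vaccination time cannot be later than it. The imputation rule and the treatment-emergence test therefore combine to exclude every non-solicited AE that the imputation places at first vaccination: unsolicited AEs, SAEs, AESIs and medically attended AEs.

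Safety is a primary objective, and the vaccination day belongs to the unsolicited AE window: SAP 10.5.4 says "Information on unsolicited AEs occurring on each vaccination day (i.e. dose 1 and 2) and the following 28 days after each dose is collected". Staff observe subjects for at least 30 minutes after the injection and record AEs (Protocol 9.1.1.1 and 9.1.2.1). Anaphylaxis is on the AESI list (SAP Appendix 2) and is not a solicited reaction. If its Day 1 record had no start time, it would be missing from the AESI tables. The uncensored repeats in SAP 12.6.1.4 and 12.6.7 would not restore it, because they lift censoring and not the restriction to treatment-emergent events.

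**Working it through.** No sample size, rate or alpha is involved, and the plan gives no figure to reproduce. The check applies the SAP 10.3 rules as written to example records, then compares the strict test (start > vaccination) with the inclusive test (start ≥ vaccination). It takes the vaccination start in SAP 10.3 to mean first vaccination. The first vaccination is set at 10 Feb 2021, 10:30. That date is only an illustration and does not affect the pattern.

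| Non-solicited AE record | Start after SAP 10.3 | Strict > | Inclusive ≥ |
|---|---|---|---|
| 10 Feb 2021, time missing | 10 Feb, 10:30 | no | yes |
| Feb 2021, day missing | 10 Feb, 10:30 | no | yes |
| 2021, month and day missing | 10 Feb, 10:30 | no | yes |
| 10 Feb 2021, timed 10:31 | 10 Feb, 10:31 | yes | yes |
| 11 Feb 2021, time missing | 11 Feb, 00:00 | yes | yes |
| Mar 2021, day missing | 1 Mar, 00:00 | yes | yes |
| Jan 2021, day missing | 15 Jan, 00:00 | no | no |
| Year missing | none | yes, by 10.5.1 | yes, by 10.5.1 |

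The first three rows are the ones at issue. A record timed at exactly 10:30 behaves in the same way. The inclusive test changes only these ties and leaves every other row as it was.

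Two features of the SAP suggest that the strict wording was not intended.

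1. **The special time rule has no effect on TEAE status at dose 1.** SAP 10.3 gives the first vaccination day its own imputed time in place of 00:00. Under a strict test, 00:00 < 10:30 fails and 10:30 = 10:30 also fails. Under an inclusive test, 00:00 fails and 10:30 passes. The rule changes treatment emergence only if ties count.
2. **Less information gives a more inclusive result.** An AE with no start year is tabulated. An AE known to have started on the vaccination day, with only the time missing, is not.

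**The case against.** The strongest reply is that no event has been shown to be lost. Imputing the vaccination time suggests that the authors meant these AEs to count, and the programs may already use ≥. Protocol 11.4 has missing or inconsistent data queried, so few such records may remain. All AEs are listed, the unsolicited AE listing flags treatment emergence (SAP 12.6.1.1), and SAEs are listed by subject (SAP 12.6.1.3). The rule is the same in all arms and no formal safety testing is planned. All of this stands, and it limits the weight of the point. It does not supply a tie rule, and a listing does not put an event back into a table.

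A reader might infer more than the documents support:

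- *That events are in fact missing from the tables.* The documents show a rule, not the programming or the data.
- *That the SAP contradicts the protocol.* Protocol 10.3.5 separates AEs after and before first vaccination and leaves the tie open.
- *That the dose 2 rule contradicts this one.* SAP 10.5.4 assigns an AE of undeterminable timing on the dose 2 day to dose 2. That rule decides which dose an AE belongs to, and such an AE already follows dose 1. It shows a more inclusive convention and is not in conflict with 10.5.1.
- *That reactogenicity data are affected.* Solicited AEs are explicitly exempt.
- *That the share of tied AEs truly starting before or after dose 1 can be estimated.* It would depend on whether AEs between consent and dose 1 are recorded, and the documents are mixed. Protocol Appendix 10 starts recording at consent, but its recording paragraph limits this to the periods in Section 9.3. Section 9.3.1 starts unsolicited AEs on the vaccination day, and SAP 10.5 says nothing beyond its own list needs recording.

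**Conclusion.** The rule is wrong as written, and the matter is minor. Followed literally, SAP 10.3, 10.5.1 and 12.6.1 together remove from the summary tables any non-solicited AE whose start ties with first vaccination, and the imputation rules create such ties in three situations. This rests on reading 'after' as strictly later, and no SAP text says otherwise.

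The size is unknown. The documents give no count of untimed Day 1 AEs or of partially dated AEs in the vaccination month or year, and the number may be small or zero. The effect is confined to non-solicited AEs tied with dose 1, and to tables rather than listings. The point still merits correction because it concerns the primary safety tables and the remedy is a short edit.

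**What to change.** In SAP 10.5.1, change 'after' to 'on or after' the date/time of first vaccination, and state that ties created by the SAP 10.3 imputation count as treatment emergent. Align the opening description of a TEAE in the same section. If the programs already treat ties this way, the edit only documents it.

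No new data are needed. The downside is that some untimed or partially dated AEs that truly began before dose 1 would be tabulated. Their share cannot be fixed from the documents. An existing SAP 10.3 rule gives some protection: an imputed start later than the resolution date is moved back to the resolution date, so an AE known to have resolved on a day before dose 1 would still be excluded. Counting the remainder is the conservative direction for safety and applies equally to all arms.

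An optional and separate wording point affects only the additional tables. SAP 12.6.7 allocates AEs by the products given before the AE start date, which, read literally, gives a treatment-emergent Day 1 AE no group. The text could allocate such an AE to the trial product given that day.
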